	APPENDIX 1: DETERMINING CHILDBEARING POTENTIAL	27
	APPENDIX 2: STUDY FLOWSHEET	28
	APPENDIX 3: DARK ADAPTATION PROTOCOL	30
	APPENDIX 4: EVALUATION OF LIGHT	31

Table of Contents (continued)

LIST OF ABBREVIATIONS

Abbreviation	Term
BCVA	Best-corrected visual acuity
CC	Clinical Center
CD	Clinical Director
CFP	Color Fundus Photography
CFR	Code of Federal Regulations
CRIS	Clinical Research Information System
CTCAE	Common Terminology Criteria for Adverse Events
Emmes	The Emmes Company, LLC
EMR	Electronic Medical Record
ETDRS	Early Treatment Diabetic Retinopathy Study
FAF	Fundus Autofluorescence Imaging
FDA	Food and Drug Administration
HRPP	Human Research Protection Program
IND	Investigational New Drug
IOP	Intraocular Pressure
IP	Investigational Product
IRB	Institutional Review Board
IU	International Unit
LLQ	Low luminance questionnaire
LLVA	Low luminance visual acuity
LORD	Late-onset retinal disease
NEI	National Eye Institute
NEI QA	National Eye Institute Quality Assurance
NEIS	National Eye Institute Support
NIH	National Institutes of Health
OCT	Optical Coherence Tomography
PI	Principal Investigator
RIT	Rod Intercept Time
RPD	Reticular Pseudodrusen
RPE	Retinal Pigment Epithelium
SAE	Serious Adverse Event
SOP	Standard Operating Procedures
USP	United States Pharmacopeia
YAG	Yttrium-Aluminum Garnet

Table of Contents (continued)

PRÉCIS

Objective: The objective of this study is to investigate the potential efficacy and safety of vitamin A palmitate dosing in improving dark adaptation in participants with age-related macular degeneration (AMD) and abnormal dark adaptation.

Study Population: The first cohort consists of five participants with AMD who meet the eligibility criteria. The second cohort will consist of five participants with AMD who meet the eligibility criteria. Up to five additional participants may be accrued in the second cohort to account for participants who withdraw from the study prior to receiving one month of study supplementation for a reason unrelated to an adverse reaction. Up to 18 participants may be enrolled in this study.

Design: This is a prospective, uncontrolled, single center, pilot study to investigate the potential efficacy and safety of vitamin A palmitate dosing in improving dark adaptation in participants with AMD and abnormal dark adaptation. Participants in the first cohort were instructed to take 16,000 IU of vitamin A palmitate daily for two months. Enrollment for Cohort 1 ended on May 24, 2019. Participants in the second cohort will be instructed to take 48,000 IU of vitamin A palmitate daily for one month. Participants in both cohorts will continue in the study for one month after ending Vitamin A supplementation. Participants in Cohort 1 may enroll into Cohort 2 as long as their last intake of vitamin A palmitate was greater than two months prior to their enrollment into Cohort 2.

Outcome Measures: For each cohort, the primary outcome is the measurement of dark adaptation parameters (thresholds and kinetics) by the following: dark adaptation times as measured by the AdaptDx comparing before and after vitamin A palmitate supplementation and dark adaptation parameters as measured by the Medmont comparing before and after vitamin A palmitate supplementation. The primary outcome will be assessed at Month 2 in the first cohort and Month 1 in the second cohort. For both cohorts, the secondary outcomes include changes in low luminance visual acuity (LLVA) and changes in patient reported outcomes as measured by the low luminance questionnaire (LLQ). The secondary outcomes also include measurement of dark adaptation parameters (thresholds and kinetics) comparing baseline and one month after completing supplementation (Month 3 in Cohort 1 and Month 2 in Cohort 2).

1.0 INTRODUCTION/SCIENTIFIC RATIONALE

Age-related macular degeneration (AMD) has been the leading cause of central vision loss in people age 65 or older in developed countries^{1,2}. Decreases in central vision from late AMD is well-established, and even intermediate AMD can display small but statistically significant reductions in central acuity compared with those without AMD³⁻⁵. However, earlier cell changes accompanying AMD have direct links to additional measures of retinal function. Histopathological examination of eyes from patients with AMD has demonstrated preferential loss of rods in the photoreceptor layer of the retina with cones persisting as the last surviving photoreceptors⁶⁻⁸. Studies employing multiple approaches to measure rod and cone function have documented preferential reduced rod function in eyes with AMD⁹⁻¹⁴. A focal dark adaptometer able to focus on areas 0.5 to 3 mm from the fovea, areas thought to have earliest rod loss, has demonstrated impairments in eyes with non-advanced AMD compared to older eyes without AMD, even when visual acuity varied little between severity groups¹¹. Increasing AMD severity was associated with increased rod intercept time (RIT), an outcome of dark adaptation, with eyes having reticular pseudodrusen (RPD) demonstrating the most significant delays¹¹.

Interpreting the data on dark adaptation across different phenotypes of macula, there are several possible hypotheses that have been proposed in the literature. A testable hypothesis proposed in the literature is that the sub-RPE (retinal pigment epithelium) deposits act as diffusion barriers for entry of sufficient vitamin A into the photoreceptors. This would lead to a local deficiency or a form of nutritional deprivation at the level of the photoreceptor. Vitamin A deficiency has long been known to cause night blindness with rod dysfunction and while these patients are not deficient based on serum levels, there still could be a local deficiency at the level of photoreceptors. Without available vitamin A (due to a serum deficiency or local deficiency) to combine with opsin, photoreceptors cannot regenerate functional visual pigment at the normal rate after light exposure leading to a slowing of dark adaptation.

A first step in understanding the pathophysiology identified by abnormal dark adaptation would be to supplement eyes with abnormal dark adaptation with vitamin A palmitate. Restoration or improvement of visual function while on supplemental vitamin A palmitate would provide data to support this hypothesis in the setting of AMD. Jacobson et al¹⁵ tested this hypothesis in patients with Sorsby's fundus dystrophy and demonstrated that vitamin A palmitate

supplementation could restore dark adaptation in these patients using 50,000 IU vitamin A palmitate for one month, but was also able to show maintenance of some (but not all) aspects of dark adaptation with 5,000 IU vitamin A palmitate¹⁵. Ayyagari and Sieving et al¹⁶ demonstrated that the dark adaptation of patients with late-onset retinal disease (LORD) with mutations in CTRP5 could be shifted with 15,000 IU vitamin A palmitate within two months of supplementation. Owsley et al¹⁷ initiated investigation into this question in older adults with early AMD and the results demonstrated that a short-term, high-dose course of preformed vitamin A increased the rate of rod-mediated dark adaptation. However, this hypothesis could be investigated with greater depth using more refined fundus phenotyping and psychophysical testing.

The preliminary analysis of the data from Cohort 1 in the DA VitA study shows that 16,000 IU of vitamin A palmitate per day was well tolerated with no adverse events requiring discontinuation of the study product. Given the previously demonstrated efficacy of vitamin A palmitate supplementation in the treatment of Sorsby's fundus dystrophy¹⁵ and eyes with early AMD¹⁷, the introduction of a second cohort that will take an increased dose of vitamin A palmitate (48,000 IU per day) in the DA VitA study is necessary since the data show that Cohort 1 did not present significant improvement in dark adaptation after taking 16,000 IU per day. The knowledge gained would provide further insights into pathogenesis of age-related macular degeneration.

2.0 STUDY OBJECTIVES

The study objective is to investigate the potential efficacy and safety of vitamin A palmitate dosing in improving dark adaptation in participants with AMD and abnormal dark adaptation.

3.0 PARTICIPANTS

Five participants with AMD who met the eligibility criteria were enrolled into the first cohort. Enrollment for Cohort 1 was halted on May 24, 2019 to focus on enrollment for Cohort 2. For the second cohort, up to five participants with AMD who meet the eligibility criteria may be enrolled in this protocol. Up to five additional participants may be accrued in the second cohort to account for participants who withdraw from the study prior to receiving one month of study supplementation for a reason unrelated to an adverse reaction. Participants in Cohort 1 may enroll

into Cohort 2 as long as their last intake of vitamin A palmitate was greater than two months prior to their enrollment into Cohort 2.

3.1 Participant Eligibility Criteria

3.1.1 Inclusion Criteria

To be eligible, the following inclusion criteria must be met, where applicable.

1. Participant must be 50 years of age or older.
2. Participant must understand and sign the protocol's informed consent document.
3. Any participant of childbearing potential (see Appendix 1 for definition) must be willing to undergo urine pregnancy tests throughout the study.
4. Any participant of childbearing potential (see Appendix 1 for definition) and any participant able to father children must have (or have a partner who has) had a hysterectomy or vasectomy, be completely abstinent from intercourse, or must agree to practice at least one acceptable method of contraception throughout the course of the study and for one week after study supplement discontinuation. Acceptable methods of contraception include:
 - Hormonal contraception (i.e. birth control pills, injected hormones, dermal patch or vaginal ring),
 - Intrauterine device,
 - Barrier methods (diaphragm, condom) with spermicide, or
 - Surgical sterilization (tubal ligation).
5. Participants must agree to notify the study investigator or coordinator if any of their doctors initiate a new prescription medication during the course of this study.
6. Participant must agree to not take $\geq 8,000$ IU vitamin A palmitate outside the study supplementation.
7. For supplementation eligibility, participant must have normal liver function as demonstrated by the Chemistry 20 panel or have mild abnormalities not above grade 1 as defined by the Common Terminology Criteria for Adverse Events v4.0 (CTCAE).
8. Participant must not be pregnant or breast-feeding and must have a negative urine pregnancy test within 24 hours prior to initiation of study medication.

3.1.2 Exclusion Criteria

A participant is not eligible if any of the following exclusion criteria are present.

1. Participant is in another investigational study and actively receiving study therapy.
2. Participant is unable to comply with study procedures or follow-up visits.
3. Participant is already taking vitamin A palmitate supplements \geq 8,000 IU.
4. Participant has a history of vitamin A deficiency.
5. Participant has a condition that, in the opinion of the investigator, would preclude participation in the study (e.g., unstable medical status including blood pressure and glycemic control).
6. Participant has a history of hepatitis or liver failure.
7. Participant has chronic gastrointestinal disease.
8. Participant will be excluded if the participant has serologic evidence of an active hepatitis infection.
9. Participant was in Cohort 1 and took his/her last dose of vitamin A palmitate less than two months prior to enrolling in Cohort 2.

3.2 Study Eye Eligibility Criteria

The participant must have at least one eye meeting all inclusion criteria and none of the exclusion criteria listed below.

3.2.1 Study Eye Inclusion Criteria

1. The eye must have a best-corrected ETDRS visual acuity score better than or equal to 20/80 (i.e., equal to or better than 54 letters).
2. Participant must have at least one large druse.
3. Abnormal dark adaptation, which is defined as having an AdaptDx test with a RIT of 16 minutes or more at the screening visit. This is at least one standard deviation greater than the average normal RIT and includes room to account for variability in testing. If at any point during current testing or under a previous NEI protocol, a participant has exceeded the 40 minute test ceiling, they will have satisfied the inclusion criteria.

3.2.2 Study Eye Exclusion Criteria

1. Presence of advanced macular degeneration with central geographic atrophy or choroidal neovascularization.

2. Presence of definite reticular pseudodrusen.
3. An ocular condition is present (other than AMD) that, in the opinion of the investigator, might alter visual acuity during the course of the study (e.g., vein occlusion, uveitis or other ocular inflammatory disease, neovascular glaucoma, Irvine-Gass Syndrome, etc.).
4. Substantial cataract that, in the opinion of the investigator, is likely to be decreasing visual acuity by three lines or more (i.e., cataract would be reducing acuity to 20/40 or worse if eye was otherwise normal).
5. History of major ocular surgery (e.g. cataract extraction, scleral buckle, any intraocular surgery, etc.) within three months prior to study entry.
6. History of YAG (Yttrium-Aluminum Garnet) capsulotomy performed within two months prior to study entry.

3.3 Choice of Study Eye in Cases of Bilateral Disease

If both eyes meet the study eye eligibility criteria described above, the following criteria will be used to select the study eye for the purposes of this investigation:

1. The eye with the better visual acuity will be chosen.
2. If both eyes are equal acuity, the right eye will be arbitrarily chosen as the study eye.

4.0 STUDY DESIGN AND METHODS

This is a prospective, uncontrolled, single center, pilot study to investigate the potential efficacy and safety of taking 16,000 IU (Cohort 1) or 48,000 IU (Cohort 2) of vitamin A palmitate in improving dark adaptation in participants with AMD and abnormal dark adaptation.

4.1 Recruitment

Participants will be recruited from the NEI clinic. Participants will be initially recruited from the following protocols: the NEI screening protocol (08-EI-0102), the Ocular Natural History protocol (16-EI-0134), DA Extension (17-EI-0112), Rod Function (16-EI-0024), or DA_AMD (11-EI-0147). Eligibility will be determined by the investigator. The participants must have the presence of one large druse. Self-referral and referral from outside physicians will be permitted. If any recruitment materials are utilized, IRB-approval will be obtained prior to distribution. The projected recruitment time for five participants in the second cohort is approximately 12 months.

4.2 Screening Visit

After the consent form is signed, all potential participants will undergo a screening evaluation in the NEI ophthalmology clinic to determine whether they meet the full eligibility criteria for vitamin A supplementation. A screening visit will be used to understand the level of dark adaptation impairment and to assess the appropriateness of the participant for inclusion. The screening and baseline examinations are outlined in Appendix 2 and listed in section 4.3.1. The investigator will review the assessments and serologic testing conducted at the screening visit prior to inviting the participant to return for continuation and vitamin A supplementation.

4.3 Study Design and Procedures

The study duration will be three months for the first cohort during which participants will be instructed to take vitamin A palmitate 16,000 IU daily by mouth for two months. In the second cohort, the study duration will be two months and the participants will be instructed to take vitamin A palmitate 48,000 IU daily by mouth for one month. In addition, there will be a screening visit between 60 days and one day prior to the baseline visit. For the first cohort, the primary outcome will be assessed at baseline versus Month 2 and the secondary outcomes will be assessed at baseline versus Month 2 and baseline versus Month 3. For the second cohort, the primary outcomes will be assessed at baseline versus Month 1 and the secondary outcomes will be assessed at baseline versus Month 1 and baseline versus Month 2. For both cohorts, visits will occur at baseline, and then monthly and as clinically indicated. The study will require five visits for the first cohort and four visits for the second cohort. All visits must be conducted within a window of \pm 14 days from the target day. At each visit, the participant will undergo a review of systems, such as an assessment of headache frequency and severity, as well as an assessment of safety variables. The tests scheduled at each visit may be split and completed within seven days (including the 7th day) from the visit date. A complete ophthalmologic examination will be performed at each visit to measure outcome variables. Participants will be screened with serum for hepatitis or hepatic dysfunction. However, for caution, we will monitor liver function tests. If participants in either cohort cannot tolerate the prescribed dose of vitamin A palmitate, they will be instructed to stop taking the supplement and they will be removed from the study.

If participants are on Coumadin® (Warfarin) at enrollment, they must visit their prescribing physician to check their Coumadin® status within two to four weeks after initiating IP to have their

Coumadin® regimen adjusted if necessary (as taking vitamin A and Coumadin® can increase the chances of bruising and bleeding.)

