7.1 Participant Withdrawal Criteria

Participation in the study is strictly voluntary. Participants may choose to withdraw from this study for any reason at any time without penalty, without loss of benefits or prohibition from enrolling in other clinical protocols. All participants will be included in the analyses at the end of the study.

The investigator may withdraw a participant at his/her discretion for the following reasons:

- Investigator determination that study continuation is not in the best medical interest of the participant;
- Findings in the course of the trial that may affect willingness to participate;
- Participant requiring additional medicines that will interfere with the study supplement;
- Serious suspected adverse reaction;
- Visual acuity loss of ≥ 15 letters from baseline;
- Any other safety concerns;
- Participant unable to meet the criteria required for continued participation;
- Participant stops taking the IP before the primary outcome is assessed;
- Participant is taking daily dose of $\geq 8,000$ IU of vitamin A palmitate in addition to study supplement;
- Participant receives standard-of-care treatment for neovascular AMD in the study eye;
- Participant is unable to complete the AdaptDx™ test;
- Participant was in the first cohort and had his/her last intake of vitamin A palmitate less than two months prior to enrolling in the second cohort.

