13.2 NEI Adverse Event Review Committee

The NEI SAE Review Committee, which consists of the NEI Clinical Director and three other NEI physicians, will be responsible for reviewing any reported serious safety events, if they occur under this protocol. The Committee will review accumulating data on a semiannual basis to determine whether the study should continue. The study PI will recuse herself from discussions of this

protocol. If changes to the protocol are indicated, recommendations will be made to the NEI Director and Institutional Review Board (IRB) who will consider and act on such recommendations in a timely manner. Should any suspected serious adverse reactions occur, the NEI Clinical Director may, at his discretion, assemble the Review Committee before the scheduled date to consider if the study should go forward. In addition, if three or more participants experience non-serious suspected adverse reactions that require temporary or permanent cessation of the IP, the PI shall report this to the NEI Clinical Director. The NEI Clinical Director may convene the Review Committee before the scheduled time to consider the cessation of the study as a whole.

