3.0 GENERAL REVIEW OF STUDY DESIGN

3.1 Study Design

The DA VitA AMD study is a prospective, uncontrolled, single center, pilot study to investigate the potential efficacy and safety of vitamin A palmitate dosing in improving dark adaptation in participants with AMD (without RPD) and abnormal dark adaptation.

The study will require five visits (screening, baseline, Month 1, Month 2, and Month 3) for Cohort 1 and four visits (screening, baseline, Month 1, and Month 2) for Cohort 2. Participants in Cohort 1 will be instructed to take vitamin A palmitate 16,000 IU daily by mouth for two months from baseline through Month 2 and will continue in the study through Month 3. Participants in Cohort 2 will be instructed to take 48,000 IU of vitamin A palmitate daily by mouth from baseline through Month 1 and will continue in the study through Month 2. The screening visit must occur between 60 days and one day prior to the baseline visit while Months 1, 2 and 3 visits must be conducted within a window of \pm 14 days from the target day. The tests scheduled at each visit may be split and completed within seven days (including the 7th day) from the visit date. At each visit, the participant will undergo a review of systems, such as an assessment of headache frequency and

severity, as well as an assessment of safety variables. A complete ophthalmologic examination will be performed at each visit to measure outcome variables. If participants in either cohort cannot tolerate the prescribed dose of vitamin A palmitate, they will be instructed to stop taking the supplement and they will be removed from the study.

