5.2 Analysis Populations

The following analysis populations will be considered for this study:

Screened population: Includes all participants screened, regardless of eligibility determination / enrollment status. Participant disposition will be based on this population.

Enrolled population: Includes all participants enrolled in the study, regardless of compliance, follow-up, or treatment received. Demographic characteristics and compliance will be based on this population. Screen failures are not included in the enrolled population.

Primary analysis population: Includes all enrolled participants who receive investigational product (IP) through the treatment completion visit. The primary, secondary, and exploratory outcome analyses will be based on this population.

Safety population: Includes all enrolled participants who receive at least one dose of IP. All safety analyses will be based on this population.

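### Mandatory removal from the study for intolerance (Protocol 4.3, SAP 3.1) does not match the discretionary withdrawal in Protocol 7.1 and, followed literally, ends scheduled safety assessments for participants who react

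*Protocol*

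**What the plan says.** Protocol 4.3 covers participants in either cohort who cannot tolerate the prescribed dose: "they will be instructed to stop taking the supplement and they will be removed from the study". SAP 3.1 carries the same rule: "If participants in either cohort cannot tolerate the prescribed dose of vitamin A palmitate, they will be instructed to stop taking the" supplement, with removal from the study to follow.

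Protocol 7.1 is worded differently: "The investigator may withdraw a participant at his/her discretion for the following reasons". The reasons listed there include "Serious suspected adverse reaction" and "Participant stops taking the IP before the primary outcome is assessed".

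Protocol 13.2 sets a reporting duty, which applies "if three or more participants experience non-serious suspected adverse reactions that require temporary or permanent cessation of the IP". It does not say whether a participant who stops temporarily stays in the study or may resume.

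SAP 6.0 and Table 1 count early discontinuation of the supplement and early termination from the study on separate rows. The SAP 5.2 safety population "Includes all enrolled participants who receive at least one dose of IP".

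**The concern.** Someone who stops the supplement because of intolerance meets both the mandatory rule in 4.3 and a discretionary item in 7.1. A participant with a serious suspected reaction, by contrast, may stay in at the investigator's discretion. Two investigators could handle the same participant differently, and each could point to the protocol.

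The stake is mainly safety data. Safety is part of the stated objective, and Cohort 2 takes three times the daily dose of Cohort 1 (48,000 / 16,000 IU). If removal is applied as written, scheduled assessments end for the participants whose later course is most informative.

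**Working it through.** No figure in the plan tests this point, so the passages are set side by side first.

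| Place | Event | Consequence for the participant |
|---|---|---|
| Protocol 4.3, SAP 3.1 | Cannot tolerate the dose | Stops and is removed; mandatory |
| Protocol 7.1 | Serious suspected reaction; stopping the supplement before the primary outcome | May be withdrawn; discretionary |
| Protocol 13.2 | Three or more participants with non-serious suspected reactions needing a temporary or permanent stop | None stated; report to the Clinical Director |
| SAP 6.0, Table 1 | Stopping the supplement; leaving the study | Two separate counts |

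The firm mismatch is between the first two rows. The third row leaves a gap: neither intolerance nor temporary cessation is defined.

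**Which assessments are affected.** Inputs are from Protocol Appendix 2. The hepatic panel and serum vitamin A are drawn at screening and then at Months 1, 2 and 3, with Month 3 for Cohort 1 only. Cohort 2 therefore has two scheduled post-dose draws.

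- Month 1 window: 30 − 14 = day 16 to 30 + 14 = day 44.
- Month 2 window: 60 − 14 = day 46 to 60 + 14 = day 74.

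Removal before day 16 precedes every in-window Month 1 visit, so neither scheduled draw takes place. Between days 16 and 44 it depends on whether the Month 1 visit has already happened. The scheduled headache and papilledema checks follow the same visits. Appendix 2 has no early-termination visit. Pregnancy (7.2) is the only event with an explicit duty of follow-up to its outcome.

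**How the tables would treat the gap.** SAP 5.5 generally excludes missing observations. Table 14 (laboratory) uses as denominator the safety-population participants who completed the visit. Table 20 (papilledema, headache) uses those with a non-missing value. A removed participant drops out of both from that visit on. Tables 12 and 13 (adverse events) use the whole safety population, so the reaction itself is still counted.

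**Primary analysis population.** SAP 5.2 defines it by receipt of the supplement through the treatment completion visit, not by study status. A permanent stopper is outside it whichever withdrawal passage is followed. Someone who pauses and resumes could be classified differently. Over 30 days Cohort 2 expects 30 × 2 = 60 doses (SAP 8.1.1). The 80% compliance threshold is 0.80 × 60 = 48, which allows 60 − 48 = 12 missed doses, or 12 / 2 = 6 days. A participant who pauses for six days and resumes would be compliant and could reach Month 1 on supplement, but would be out if the pause were treated as intolerance under 4.3.

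**Size.** One participant is 1/5 = 20% of a cohort of five, or 1/10 = 10% if Cohort 2 reaches its ceiling of ten. The documents give no intolerance rate. For an assumed rate p, the chance of at least one case among five is 1 − (1 − p)^5:

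| Assumed p | At least one of five |
|---|---|
| 5% | 23% |
| 10% | 41% |
| 20% | 67% |
| 30% | 83% |

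The additional Cohort 2 accrual in Protocol 3.0 covers only withdrawals unrelated to an adverse reaction, so it would not replace such a participant.

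**The case against.** The best defence is that both documents give one and the same specific rule for intolerance, that 7.1 is a general list that does not name intolerance, and that 13.2 is a reporting trigger with no rule for the individual. A temporary pause need not mean that the dose cannot be tolerated. All of this stands as far as 13.2 is concerned: a reader might infer that three passages prescribe three different consequences for one event, and they do not. It does not remove the mismatch with 7.1, which leaves withdrawal to discretion for anyone who stops the supplement, whatever the cause.

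A second defence is that follow-up after removal is unspecified rather than forbidden. Protocol 7.0 starts adverse event monitoring after initiation and gives no end, 4.3 allows visits as clinically indicated, and SAP 5.4 uses a supplementary-visit assessment where no scheduled one exists. This also stands. A reader might infer that later safety data are certain to be lost, but the documents support only that they may be.

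Third, this is a small exploratory pilot, and Cohort 1 had no adverse event that required discontinuation. That is relevant, though it was observed at one third of the Cohort 2 dose.

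**Conclusion.** The point holds as an inconsistency in wording with a limited but real consequence for safety data. Protocol 4.3 and SAP 3.1 make removal mandatory, 7.1 makes withdrawal discretionary for overlapping events, and 13.2 leaves the participant's status after a temporary stop open. Read literally, 4.3 ends scheduled safety assessments for those who react, and the visit-based summaries then cover only participants who completed the visit. In Cohort 2, removal before day 16 could leave no scheduled post-dose hepatic panel or serum vitamin A. This assumes that no clinically indicated visit takes place.

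Two stronger conclusions are tempting. A reader might infer that membership of the primary analysis population generally turns on which passage is followed; under SAP 5.2 that is possible only for someone who pauses and resumes. A reader might also infer that all later safety tables describe only those who tolerated the dose; Tables 12 and 13 keep every reported event over the whole safety population.

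**What to change.** 1. Reconcile Protocol 4.3 and SAP 3.1 with Protocol 7.1 and 13.2, so that one statement governs a participant's study status after intolerance, after a reaction and after a temporary stop. Which rule that should be is for the sponsor and investigators; none is proposed here.
2. State in the protocol that stopping the supplement and leaving the study are separate events, as SAP Table 1 already records them.
3. Continue the already scheduled safety assessments (hepatic panel, serum vitamin A, headache and papilledema checks) for participants who stop the supplement and agree to return, and report them in the safety-population tables.

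The cost is a wording amendment to both documents and a few already planned visits for participants off supplement. No new procedures are needed. The gain is in safety data: under SAP 5.2, later dark adaptation results from a permanent stopper would reach only the safety-population summaries in SAP section 14, not the primary analysis.
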